## Social Network Intervention

**Social Network Data from Phase I & II.** Our Phase I investigation of organizational networks identified and recruited organizations providing COVID-19 services and healthcare to compose inter-organizational networks in each study region. In Phase II, we recruited individual residents' door-to-door or from community organizations in PBGs to participate in our Phase II embedded study related to self-testing and their place affiliation history. As part of the data collection, which collects data on knowledge, attitudes, and testing behaviors, individuals completed an individual-level social network survey. These participants served as the seeds for a snowball sampling recruitment approach to identify the social ties among friends, family, and coworkers, composing communication networks through which individuals' access COVID-19 related support. Further, these social network survey respondents indicated affiliations with organizations as clients or members.

We linked Phase II personal network data with the organizational network data collected during Phase I to compose multilevel network structures for each region. In addition, in Phase II, these network survey respondents nominated individuals comprising their social networks and provided their contact information. The individuals comprising the seeds' social networks were then contacted to complete the same survey (1st snowball layer), who in turn nominated persons in their own social network. Individuals nominated by the 1st layer snowball participants were then contacted to complete the same survey (2nd snowball layer), but were not asked to identify their own social network. Nominated individuals were contacted by NetCollect software through email/messenger to complete a survey. Note that each household is a single node in the network, and while each seed can nominate and provide contact information for any individual in any number of households, they are limited to nominating one person per household.

**Social Network-Informed Intervention.** We used the data gathered in Phases I and II regarding the social networks by region to identify nodes (individuals and organizations) with the greatest influence operationalized as specific network positions they occupy in Phase I and Phase II social networks in each region. We will approach the organizations that demonstrated influence to either let their constituents know about the study or allow us to partner with them and recruit from their location. We posit this strategy will enhance the impact of the reach and impact of intervention strategies.

## Project Materials

### Intervention Arms:

**Multilevel Community Just-In-Time Network informed Adaptive Intervention (MC-NET-JITAI):** As previously described, recruitment of participants to the MC-NET-JITAI will take place at the participant's home or at one of the salient community organizations that our participants look to and interact with around COVID-19 topics identified through the social network data. CHWs will consent and enroll participants in the MC-NET-JITAI from the randomized PBGs. MC-NET-JITAI will include Community Health Workers (CHW) providing the participant with a batch of 4 rapid antigen tests that can be shared with people in the household or other close contacts if needed, a COVID-19 resource flier tailored to the study region and updated information about COVID-19 testing and vaccination. The intervention will consist of enhanced behavioral and educational text messages, up to three messages each week, providing updates on COVID-19 testing and vaccination. The text messages will include digitally-delivered intervention content such as a video with low-literacy instructions for administering the rapid antigen tests, guidance if they tested positive (e.g., quarantine, notify contacts, wearing a mask), and other relevant strategies and content focused on increasing COVID-19 testing and vaccination. The CHWs will also be available by phone to the participants for any follow-up questions. CHW will follow up via text, email and/or phone with the participants during the two months post-enrollment. In addition to the intervention, the participants will be asked to complete the pre and post-test surveys. Post surveys will be administered online, over the phone, or in person two months after the initial intervention.

### Control Arm:

**Control PBGs:** Since we are utilizing a historical control study design, we are not recruiting any new control participants for this Phase III main study. Instead, we will analyze the survey data already collected from the Phase II embedded study control participants.

### Ethics

Participants will be approached at their home or at a community organization/event for enrollment. The trained community health workers will explain the study generally and ask if the participant would like to

hear more about the study. If so, the community health worker will review the consent document and answer any questions. The participant will decide whether or not to participate and sign the documents indicating consent. A copy of the consent will be provided to the participant. The consent forms will be stored separately from the data to protect the privacy of the subjects. A unique identifier will be created to link the baseline and follow-up surveys.

The protocol for this study will also be reviewed by UTHealth - Tyler as several investigators are from this institution and one of the three study sites is in the North East Texas / Tyler region.

## **Data Management and Security**

### **REDCap (Research Electronic Data Capture)**

REDCap is a secure web application for building and managing online surveys and databases. REDCap was developed by experts at Vanderbilt University with partial funding from NIH.

REDCap was designed to allow researchers with a robust data management plan to quickly define project-specific data capture forms and launch protocol in an accelerated period of time. Research projects are inherently diverse and are developed independently by investigative teams across the spectrum of biomedical sciences. As such, these projects tend to have diverse data dictionaries to represent common data elements such as demographics, clinical findings, and laboratory results. Providing pre-built, shared forms may shorten the database development process while promoting harmonization of data collection. Although data collection form creation is straightforward in REDCap, researchers relayed early in the program their desire to reuse validated instruments developed previously by their own teams or by other research teams in the consortium. In addition to saving setup time for research studies, creating easily consumable, pre-defined data collection instruments from a shared library would facilitate the harmonization of data collection across multiple studies since they would be using a common data dictionary.

We used these REDCap features to collect data from CHWs, tracking Phase III recruitment and collecting survey responses from enrolled participants.

REDCap data capture system is fully compliant with the FDA regulatory requirements. REDCap can be installed in a variety of environments for compliance with such standards as HIPAA, 21 CFR Part 11, FISMA (low, moderate, high), and international standards. REDCap is fully personalized to meet your security policies and user needs. The REDCap uses PHP + JavaScript programming languages and a MySQL database engine for data storage and manipulation. The system runs in Windows/IIS and Linux/Apache web server environments. The diverse applications of REDCap include support of basic science research studies, data collection for clinical trials, registries and cohort studies, quality reviews for clinical practice, comparative effectiveness trials, patient questionnaires, clinical decision support applications, and operational support. REDCap provides automated export procedures for seamless data downloads to Excel and common statistical packages (SPSS, SAS, Stata, R), as well as a built-in project calendar, a scheduling module, ad hoc reporting tools, and advanced features, such as branching logic, file uploading, and calculated fields.

## Data Collection

The front-end web app will be accessible to external users on the UTHealth School of Public Health web domain at <https://redcap.uth.tmc.edu/>. Project staff will be provided login credentials specific to their role. For instance, the research coordinator for the survey will have full administrative control over the local application and datasets stored in the back-end server, including the ability to create new projects, modify project components, adjust the survey programming, and export survey results in various formats at any time. “Lead” users will be able to initiate surveys, open and close surveys for editing, and send reminders to participants automatically via phone or email. “Leads” will also be able to track the progress of other projects, and staff during “Interviewers” will be able to navigate the application to administer surveys and to track recruitment following the procedures described above.

The project coordinator responsible for REDCap will perform quality assurance and quality control checks on the database collected weekly to identify inconsistent data points, missing data, and incomplete data collection.

Two forms will be prepared for each region. One form will be to administer and collect the Phase III main study survey among enrolled intervention participants and will be initiated by project staff in person upon enrollment. We will also use REDCap to administer follow-up surveys two months after the participant completes their first survey, which will be done during a phone call or in person with a staff member who records the responses. After multiple attempts to complete the survey via phone or in person, we will reach out to the study participant with a secondary option to complete the follow-up survey via email or text message.

All surveys initiated in REDCap will have a unique survey identifier for the individual participant and the region where the survey is taking place and will be automatically anonymized. Phase III main study survey responses will also be iterated with proper data points identifying the census block group where the participant was recruited.

All recruitment data and survey data collected for the Phase III main study will be recorded and maintained within REDCap at UTHealth per funder requirements. This dataset will include the funder required RADx Common Data Elements (CDEs) and additional measures assessing the primary outcomes of testing behaviors and their psychosocial and socioeconomic determinants. Additional quality assurance and quality control procedures will be completed on the CDEs per funder requirements and then uploaded on a regular schedule to the RADx-UP Coordination and Data Collection Center (CDCC). The data will be shared with the Duke Clinical Research Institute (“DCRI”) in North Carolina. Duke was chosen by the NIH to hold the data from all RADx-UP studies. Duke will keep these non-identifiable data in a secure database for COVID-19 research at the NIH.

We are handling the data management and monitoring according to Good Clinical Practice Guidelines. This will ensure we meet the ethical and scientific quality standards for conducting trials (GCP) guidelines. The principles of GCP help to ensure the quality and consistency of trial/study operations and data and may result in increased costs.

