Upon completion of the baseline survey part A, the participant will receive the first incentive card valued at \$50. Study personnel will also make an appointment for the 8 weeks follow-up post-survey to be conducted by phone (or in person, depending on participant preference) and obtain contact information to follow up throughout the 8 weeks period with intervention related messages or answer participant questions. The staff will send a reminder of the 8 weeks follow-up appointment to the participant. The time frame for the follow-up appointment will be determined by study personnel counting out 8 weeks from the initial home visit. However, because the participant's schedule and availability will be accounted for, the earliest this follow-up appointment can be completed will be 5 weeks from the initial visit and as late as the last day of data collection for that PBG, which could be approximately 4 months from the initial visit. The week and day prior to the post-survey appointment, study personnel will send reminders. The phone-based post-survey will take up to 30 minutes, and the participant will be issued a second incentive card valued at \$35 for their participation in the post survey, which will be mailed or emailed to the participant by study personnel if the follow-up was done via phone. If the participant prefers, the follow-up appointment can be completed in person instead of over the phone, and the incentive will be given in person as well.

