### Sample Size for Testing the primary hypothesis in this study.

We have estimated the sample size of the prospective cohort based on the primary hypothesis that individuals experiencing the intervention of Phase III will have higher levels of effective use of SARS-CoV-2 testing than their testing at baseline. The McNemar test, together with the odds ratio (OR) of COVID-19 testing for post-intervention versus baseline, will be used to assess the intervention effect. Preliminary data yielded a discordance of 19% between baseline and follow-up measurements. The ORs were 3.4, 2.3, and 2.3 for Harris, Cameron, and NETX, respectively. The OR for the pooled data was 2.55. We use an OR of 2.5 and a discordance of 19%, which represents an 8% difference in the proportion of testing at follow-up compared to baseline, to size the prospective cohort. For a one-sided test at the significance level of 2.5%, a **sample size of 237 is needed to provide 80% power** for confirming the intervention effect. To allow for a **45% loss to follow-up**, 431 participants need to be enrolled at baseline. The table below provides the size options for a one-sided McNemar test of alpha 2.5% and power 80%.

Proportion of discordance	Odds ratio (OR)	Difference in proportion of testing pertaining to OR	Required sample size	Enrollment allows for a 35% loss to follow-up	Enrollment allows for a 45% loss to follow-up
0.19	2	6%	393	605	715
0.19	2.5	8%	237	365	431
0.19	3	9.5%	177	273	322
0.3	1.5	6%	681	1048	1239
0.3	1.727	8%	387	596	704
0.3	2	10%	249	384	453
0.3	2.75	14%	128	197	233

**Statistical Analysis - MC-NET-JITAI.** We will analyze the secondary outcome measures using the McNemar test, conditional logistic regression model, generalized linear mixed model (GLMM). The enrolled individuals completing the follow-up survey constitute the analysis set. In GLMM, we will specify proper random effects to account for hierarchical nesting structure. Secondary analyses will examine the relation between knowledge, attitudes, and intentions on testing and vaccination decisions and we will use the same multilevel GLMM models.

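### The primary testing outcome is analysed only for people who complete the whole follow-up survey, and the plan describes no shorter way to collect it

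*Combined protocol and SAP*

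**What the plan says.** The section on primary and secondary outcome measures takes the testing outcome from the pre-post surveys and names no other source. Under Recruitment, follow-up is an appointment by phone or in person: "The phone-based post-survey will take up to 30 minutes". Under Data Collection, after multiple failed attempts the participant gets "a secondary option to complete the follow-up survey via email or text message". The Intervention Arms section lists the modes without an order: "Post surveys will be administered online, over the phone, or in person two months after the initial intervention". No section describes a shortened form or a contact limited to the primary outcome.

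The analysis rule appears in the same words in the missing-data item of Data Monitoring and Data Management and in the MC-NET-JITAI analysis paragraph: "The enrolled individuals completing the follow-up survey constitute the analysis set". There is no rule for partly completed surveys.

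A smartphone that accepts texts is an inclusion criterion (Study Population), and participants are sent up to three intervention texts a week (Intervention Arms). The sample size section plans for 45% loss to follow-up.

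**The concern.** Membership of the analysis set depends on finishing a survey, not on having the primary outcome. A participant who tires of a long call, or opens the link and stops halfway, contributes nothing to the primary analysis even if the testing questions were answered. A participant who would answer a question or two by text, but not a whole survey, is never asked. Yet the study already holds a working text channel to everyone it enrols.

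The main test is a within-person comparison of follow-up with baseline. If people who do not finish the survey changed their testing less than those who do, the completer estimate overstates the change in the enrolled cohort. With 45% loss planned, the room for this is large. Enrolling more people to offset the loss protects power but does nothing about selection.

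**Working it through.** **Inputs**, all from the sample size section: "For a one-sided test at the significance level of 2.5" per cent; "sample size of 237 is needed to provide 80% power"; "We use an OR of 2.5 and a discordance of 19" per cent, "which represents an 8% difference in the proportion of testing at follow-up compared to baseline"; 45% loss; 431 enrolled.

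**1. Reproduce the plan's figures.** With discordance 0.19 and odds ratio 2.5:
- Favourable discordant proportion = 0.19 × 2.5/3.5 = 0.1357.
- Unfavourable = 0.19 × 1/3.5 = 0.0543.
- Net gain = 0.1357 − 0.0543 = 0.0814, the plan's rounded 8%.

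The exact conditional McNemar test, with power averaged over a binomial(n, 0.19) number of discordant pairs, first reaches 80% at n = 237 (power 0.8001). Enrolment is 237/0.55 = 430.9, so 431. Both figures stand.

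**2. Outcomes lost.** 431 − 237 = 194, or 45%.

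**3. Effect in all enrolled.** Gain = 0.55 × 0.0814 + 0.45 × (change in the lost). The documents do not give the change in the lost, so a range is assumed.

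| Net change in the 194 (assumed) | Gain in all enrolled |
|---|---|
| +8.1 points (same as completers) | 8.1 points |
| +4 points | 6.3 points |
| 0 | 4.5 points |
| −4 points | 2.7 points |

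**4. What a short form could recover.** The documents give no recovery rate. Assume 15% to 30% of the 194, which is 29 to 58 people. Pairs observed become 237 + 29 = 266 to 237 + 58 = 295. Missingness falls to (194 − 29)/431 = 38% to (194 − 58)/431 = 32%.

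**5. Effect on power.** This uses the same exact test with overall discordance held at 0.19. The average net gain is (237 × 0.0814 + r × f × 0.0814)/(237 + r), where r is the number recovered and f is the fraction of the full effect they show. The probability that a discordant pair is favourable is (0.19 + average gain)/(2 × 0.19).

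| Effect in the recovered | Power, n = 266 | Power, n = 295 |
|---|---|---|
| Full (f = 1) | 84.8% | 88.5% |
| Half (f = 0.5) | 80.2% | 80.6% |
| None (f = 0) | 74.9% | 70.1% |

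The 4.5-point figure and the 85% to 88.5% power figures cannot be quoted together: the first assumes no net change in the lost, the second assumes the full effect. Under the no-change assumption, power falls below the planned 80%.

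**The case against.** **Retention is already addressed.** The plan offers a choice of mode, reminders the week and the day before, a $35 incentive, a window from 5 weeks to about 4 months, community health worker contact, a survey link and weekly checks for incomplete data. Informative missingness is to be modelled. This stands as a description. But every one of these measures still ties the testing outcome to the whole survey. The modelling is conditional, names no model, recovers no outcome and sits beside a completers-only set.

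**Recovery is uncertain.** The people targeted have already not responded to repeated attempts and a link, and the weekly texts are described as outgoing content. This stands; the 15% to 30% is an assumption. The analysis-set rule is worth changing even if nobody replies.

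**Stronger readings that the documents do not support.** A reader might infer any of the following:
- *The loss favours the intervention against controls.* The historical controls are also restricted to people with both surveys (General Information; Study Design), and their attrition is not given, so the direction is unknown.
- *Less engaged people test less, so the pre-post result is biased.* A lower level of testing does not by itself bias a paired change; these people would have to change less.
- *The primary outcome is a single question.* The table of survey constructs lists several testing questions, and the survey is an attachment not available for this review. That the link carries the full survey likewise rests on the Data Collection wording.
- *The sections conflict on follow-up mode.* They can mostly be reconciled, because Data Collection gives an order.
- *Baseline was staff-recorded and follow-up may not be.* Part A was recorded by staff, but Part B was sent for self-completion, and the documents do not say which part holds the testing items.

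**Conclusion.** The point holds as a weakness in design and analysis-set definition, not as an error in the sample size. Under the plan's own allowance, 194 of 431 enrolled people have no primary outcome, and no route to it exists short of the whole survey. If those 194 had no net change, an 8.1-point gain in completers is 4.5 points in the enrolled cohort. That figure rests on an assumption about unobserved people and shows the possible size of the bias, not an estimate of it.

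The benefit of the remedy is less missing data and less potential for selection bias in the pre-post result. More power is not a reason to adopt it: depending on how the recovered people changed, power could rise to about 85% to 88.5%, stay near 80%, or fall to 75% to 70%. The change is inexpensive relative to the planned missingness and should be made.

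**What to change.** - **Analysis set** (missing-data item and MC-NET-JITAI analysis paragraph): for each outcome, include everyone with that item at baseline and follow-up, whether or not the survey was finished.
- **Short form** (Data Collection): if the full-survey link also fails, send a final short REDCap form by text or email with only the primary testing item(s) and the vaccination item, worded as in the survey.
- **Order of modes:** align Recruitment and Intervention Arms with the order in Data Collection.
- **Sensitivity analyses:** record the mode and form of each follow-up. Repeat the primary pre-post analysis in interviewer-collected follow-ups only. Repeat the historical-control comparison in full-survey completers only, so that both groups are selected alike.

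The cost is one short form, a field for mode and form, and protocol and SAP wording. The drawbacks are that short-form responders have no psychosocial data, some outcomes are self-completed, and these responders are selected differently from the completer controls. The two sensitivity analyses address the last two; the missing psychosocial data should be accepted and reported.

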## Data Monitoring and Data Management

The quality of a clinical study is ultimately dependent on the integrity of the data collected during the study. Well-organized and reliable data are critical to the success of a study. Data management procedures are performed to maintain data integrity and to ensure the data generated during the study will arrive at the same conclusions and interpretations equivalent to those derived from clean data. This process includes 1) Data Monitoring, 2) Data Cleaning, 3) Missing data, and 4) Quality Control checks.

- 1) **Data Monitoring:** The RDCC has the overall responsibility for the trial's data monitoring. The RDCC personnel regularly conduct data monitoring to identify potential discrepancies in the data and communicate with the clinic to resolve the discrepancies. The primary focus for data monitoring is critical to protect human subjects, maintaining the integrity of study data, and compliance with applicable regulations. We will be devoted to assessing the critical study data and processes and evaluating significant risks and potential site non-compliance identified. Identify data entry errors (e.g., discrepancies between source records and case report forms (CRFs) and missing data in source records or CRFs; Verify that the study documentation exists (e.g., consent process is documented, etc.). Monitor the quality of the overall conduct of the trial at the study site (e.g., attention to detail, thoroughness of study documentation, appropriate delegation of study tasks, and appropriate investigator supervision of clinic staff performing critical study functions). In addition, we assess compliance with the protocol and investigational product accountability. A data monitoring report will be sent to the research coordinator and the PI. The monitor should follow up with the clinical site to ensure that the issues raised by the monitor are addressed in a satisfactory manner. The recommendations provided by the monitor are meant to ensure compliance and data quality and improve site practices that could result in inadequate human subject protection and/or poor data quality.
- 2) **Data Cleaning:** The RDCC Data Management group will conduct data cleaning for the trial. Data cleaning refers to a group of activities used to assure the completeness, validity, and accuracy of data. Data cleaning activities are including a) developing and running various rules to identify potential anomalies in the data submitted by the sites, b) creating an Edit Check Program (ECP) is created in SAS that check for missing data, implausible data (that which complies with the codebook but is not in the range/suspect), improbable data (potential outliers' lab values (Mean $\pm$ 5SD)), or for other measurements with normal distributions (Mean  $\pm$ 3SD). For skewed distributions this could vary between 4 SDs and 5 SDs, impossible data (does not comply with the codebook /incorrect), and c) protocol deviations. The participant information on paper CRFs and data entry into database will be done by research assistant/coordinator once the participant was enrolled in to the study and the initial study data collection is complete. Once the data are in the database, the Data Management Analyst at RDCC runs the ECP periodically, which checks that all required data in CRFs are entered into the database. The ECP will also look for missing and discrepant data. The list of missing and discrepant data will be communicated to research coordinator and the PI and sent for further checking/correction; any corrected data will again be entered into the database. Data cleaning will be done periodically (biweekly/monthly) until the errors are amended as an iterative process. The database is equipped to have audit trail. In this trial, we will also use Census data at the Block Group level to obtain certain information that is not available at individual level. This necessitates careful attention when merging data at individual and Block Group levels. The Census data at Block Group level is de-identified. [name] has worked on grants focused on assessing Social Disparities in Health using Measurement of Neighborhood Socioeconomic Characteristics.

- 3) **Missing data:** The enrolled individuals completing the follow-up survey constitute the analysis set. Every effort will be made to keep all participants in the study and to obtain required data at each scheduled time point. All information for patients who dropped out from the study will be recorded and stored in the database. Traditional regression techniques usually assume that all data are complete and will produce unbiased estimates and valid inferences under missing completely at random (MCAR) assumption. We will examine drop-outs, missing data and measurement errors which are common problems with longitudinal data structure to be able to identify accurate missing data mechanisms and patterns so that we can explain missing data mechanism. If the missing data are non-ignorable/informative in the sense that missingness may depend on the missing observations, modeling of the informative missing data or dropout processes will be conducted. An attempt will be made to incorporate the missing values mechanism into the model as discussed in Little and Rubin. All Analyses will be performed primarily using widely available tools in SAS® version 9.4 (SAS Institute, Cary, NC) or R, at a significance level of 0.05.
- 4) **Quality Assurance (QA) & Quality Control (QC) Procedure** Upon completion of resolving data cleaning, the data quality control process will be initiated. The QC process involves 1) randomly selected patients (10-20%), 2) comparing source documents to CRFs, and 3) comparing CRFs with the database. In all processes, we will select critical variables that determine the safety/effectiveness of what will be used in statistical analysis.

**Data Safety and Monitoring Board (DSMB)** If needed, a Data Safety and Monitoring Board will be established to oversee the conduct of this study to ensure participant safety and quality of the data. The DSMB will be convened to monitor activities conducted at all intervention and control sites, and to oversee data collection and implementation at all community and clinic organizations. The functions of the DSMB include the following: 1) To review and approve a plan for data quality assurance and safety monitoring for this trial, 2) To review data on a timely basis, to ensure proper conduct and progress of the study, 3) To review credentials of all project staff and consultants with relation to data quality and safety, 4) To make recommendations to project investigators and staff regarding issues of concern, 5) To review and address any potential ethical issues, 6) To approve any changes made in response to recommendations made by the DSMB, and 7) To alert NIH to any concerns that are not properly addressed by the study investigators.

